### **3.3            Inclusion of Women and Minorities**

Both men and women of all races and ethnic groups are eligible for this trial.

#### **4. REGISTRATION PROCEDURES**

##### **4.1 General Guidelines for DF/HCC Institutions**

Institutions will register eligible participants in the Clinical Trials Management System (CTMS) OnCore. Registrations must occur prior to the initiation of any protocol-specific therapy or intervention. Any participant not registered to the protocol before protocol-specific therapy or intervention begins will be considered ineligible and registration will be denied.

An investigator will confirm eligibility criteria and a member of the study team will complete the protocol-specific eligibility checklist.

Following registration, participants may begin protocol-specific therapy and/or intervention. Issues that would cause treatment delays should be discussed with the Overall Principal Investigator (PI). If the subject does not receive protocol therapy following registration, the subject must be taken off-study in the CTMS (OnCore) with an appropriate date and reason entered.

###### **4.1.1 For Enrollment to Arm 1 or Arm 2 (Randomized Trial Arms)**

The eligibility checklist(s) and all pages of the consent form(s) will be faxed to the ODQ at [contact]. The ODQ will (a) review the eligibility checklist, (b) register the participant on the protocol, and (c) randomize the participant.

**Randomization can only occur during ODQ business hours (8:30 am – 5 pm Eastern Time, Monday through Friday excluding holidays).**

An email confirmation of the registration and/or randomization will be sent to the Overall PI, study coordinator(s) from the Lead Site, treating investigator and registering person immediately following the registration and/or randomization.

##### **4.2 Registration Process for DF/HCC Institutions**

Applicable DF/HCC policy (REGIST-101) must be followed.

##### **4.3 General Guidelines for Non-DF/HCC Investigative Sites**

Eligible participants will be entered on study centrally at the Dana-Farber Cancer Institute by the Project Manager or Study Coordinator. The required forms can be found in **Section 4.4**.

Following registration, participants should begin protocol therapy within 7 days. Issues that would cause treatment delays should be discussed with the Overall PI. If the subject does not

receive protocol therapy following registration, the subject must be taken off-study in the CTMS (OnCore) with an appropriate date and reason entered.

#### **4.4 Registration Process for Non-DF/HCC Investigative Sites**

To register a participant, the following documents should be completed by the participating site and faxed or e-mailed to the Study Coordinator/Project Manager:

- Signed participant consent form
- HIPAA authorization form
- Eligibility checklist
- Screening provider note including the medical/surgical history, ECOG performance status, vital signs, and physical exam findings
- Pathology report confirming adenocarcinoma or poorly differentiated carcinoma of the pancreas
- Laboratory reports including:
  - CBC with differential
  - Chemistry panel
  - Pregnancy test (if applicable)
- Screening imaging report (CT and/or MRI scans)
- Screening ophthalmic exam report
- Screening EKG

To complete the registration process, the Project Manager or Study Coordinator will follow DF/HCC policy (REGIST-101) and register the participant on the protocol. The registering party will fax or email the participant study number and assigned arm or dose treatment level to the participating site.

**NOTE: Registration can only be conducted during the regular business hours of 8:30 AM to 4:30 PM Eastern Standard Time Monday through Friday, holidays excluded.** Same day treatment registrations will only be accepted with prior notice and discussion with the DF/HCC Project Manager or Study Coordinator.

### **5. TREATMENT PLAN**

#### **5.1 Treatment Regimen**

A treatment cycle will be defined as 28 consecutive days. Treatment will be administered on an outpatient basis. Reported adverse events and potential risks are described in **Section 7**. Appropriate dose modifications are described in **Section 6**.

##### **5.1.1 Safety Lead-in Cohort**

To confirm the safety of the LY3214996 and HCQ combination, a lead-in cohort will be conducted. The first six participants will enroll to **Dose Level 0**, as depicted in the table below. Enrollment to the dose level can occur in parallel with no observation period or delay between

the start of therapy for each enrolled participant.

| Table 2: Safety Lead-in Cohort Dose Plan |                           |   |
|--|---------------------------|---|
| Dose Level                               | LY3214996 Dose (mg PO QD) | Hydroxychloroquine (HCQ) Dose (mg PO BID) |
| -1 ( Fallback Dose )              | 400*                      | 200*                                      |
| 0  | 400                       | 400                                       |

\*: At the discretion of the overall principal investigator, the fallback dose of LY3214996 may be reduced to 200 mg PO QD instead of or in addition to a reduction of the HCQ dose level. The principal investigator determined dose level -1 to be LY3214996 200 mg PO QD and HCQ 400 mg PO BID

Participants will be observed during the first cycle of therapy for toxicity consistent with a dose-limiting toxicity (DLT) definition, defined in **Section 5.1.2**. If  $\leq 1$  DLT is observed among the six participants, the randomized two arm portion of the trial will begin with enrollment to Arms 1 and 2 (see **Section 5.1.3**).

If **Dose Level 0** is found intolerable (with  $\geq 2$  participants experiencing a DLT), **Dose Level -1** will be evaluated. If **Dose Level -1** is also not tolerable, the cohort will be closed with no further combination treatment enrollment and the trial will proceed as a single arm evaluation of LY3214996 as monotherapy.

| Table 3: Dose Escalation Decision Criteria for Safety Lead-in Cohort |  |
|--|--|
| Number of Participants with DLT at a Given Dose Level                | Escalation Decision Rule   |
| $\leq 1$   | Proceed with enrollment to the randomized two arm portion of the trial.  |
| $\geq 2$   | Enrollment to the dose level will be stopped. This dose level will be declared the MAD (highest dose administered). Proceed with enrollment of six participants to the fallback dose level if at Dose Level 0 . If at Dose Level -1 , enrollment to combination treatment will be stopped. |

Participants enrolled to the safety lead-in portion of the trial will be required to have received at least 75 percent of their assigned doses of LY3214996 and HCQ during the first cycle to be considered evaluable for DLT purposes. Participants will be replaced if they do not meet these parameters during cycle 1 for reasons other than toxicity (e.g. withdrawal of consent for participation, or rapid disease progression and subsequent removal from the trial).

### 5.1.2 Dose-Limiting Toxicities (Applicable for Safety Lead-in Cohort Only)

DLTs will be defined as toxicities experienced by participants enrolled in the safety lead-in that are considered at least possibly related to the treatment regimen, occur during the first cycle of treatment, and fit at least one of the following criteria:

- Grade 4 absolute neutrophil count (ANC) decrease of greater than 7 days duration, or ANC decrease that necessitates the use of growth factor support
- Febrile neutropenia
- Grade 3 thrombocytopenia with clinically significant bleeding, or that requires transfusion support
- Grade 4 thrombocytopenia
- Grade 4 anemia
- Intolerable Grade 2 nausea or vomiting that is unresponsive to maximal medical management (see **Section 5.4** for anti-emetic regimen information).
- Any  $\geq$  Grade 3 non-hematologic toxicity, with the following exceptions:
  - Grade 3 gastrointestinal toxicities (nausea, vomiting, diarrhea, or constipation) that were not optimally managed. Grade 3 gastrointestinal toxicities will only be considered dose-limiting if refractory to treatment, defined as a failure to resolve to  $\leq$  Grade 2 or baseline within 48 hours of instituting appropriate supportive care.
  - Grade 3 rash that resolves to  $\leq$  Grade 2 within 7 days and remains tolerable may not be considered a DLT if agreed upon with the overall principal investigator.
  - Grade 3 asymptomatic electrolyte abnormalities that resolve to  $\leq$  Grade 2 or baseline within 48 hours of repletion/clinical intervention.
- Any death not clearly due to underlying disease or extraneous causes.
- Any toxicity that results in the participant receiving  $< 75\%$  of the **assigned** doses of LY3214996 or HCQ during cycle 1.

Management and dose modifications associated with the above adverse events are outlined in **Section 6**.

#### 5.1.3 Arm 1 and Arm 2

If combination dosing with LY3214996 and HCQ is found tolerable ( $\leq 1$  DLT among 6 participants enrolled to the dose level), the randomized two arm portion of the trial will commence. Participants will be randomized 1:1 to enroll to either **Arm 1** or **Arm 2**.

##### 5.1.3.1 Arm 1 Treatment: LY3214996 + HCQ

If **Dose Level 0** was found tolerable, enrollment to **Arm 1** will initiate with LY3214996 at a dose of 400 mg PO daily and HCQ at 600 mg PO BID. Following accrual of six evaluable participants to **Arm 1**, enrollment to **Arm 1** will be paused for an assessment of safety of the increased dose of HCQ.

The safety assessment will occur after all six participants on **Arm 1** have completed at least one cycle of dosing with the combination. Participants must have received at least 75% of their assigned doses of LY3214996 and HCQ to be considered evaluable for this safety analysis, unless dosing was held or reduced due to toxicity. If one or more of the first six participants enrolled does not meet this parameter for a reason other than toxicity (e.g. rapid disease progression and subsequent removal), **Arm 1** will continue to accrue as many participants as needed to have six evaluable participants for safety assessment. **Participants will be replaced in**

***the randomized portion of the trial if they withdraw consent for participation before initiating protocol therapy or rapid disease progression limits their ability to receive any therapy per protocol.*** All participants accrued to the arm who start protocol treatment will be considered evaluable for efficacy endpoints, regardless of whether they meet criteria to be considered evaluable for assessment of safety of the increased dose of HCQ.

The overall principal investigator will review applicable adverse event data and determine if enrollment should continue with HCQ at the 600 mg dose level. At the discretion of the overall principal investigator, the dose level may be reduced for all participants remaining to be accrued to the arm.

If **Dose Level 0** was not tolerable, but **Dose Level -1** was tolerable, enrollment to **Arm 1** will be initiated with LY3214996 200 mg PO QD and HCQ600 mg PO BID. An interim safety assessment will still occur in this scenario. If **Dose Level -1** was also not tolerable, **Arm 1** will not move forward. The trial will proceed with enrollment to **Arm 2** only, evaluating LY3214996 as monotherapy.

**At the conclusion of the safety lead-in cohort, on March 26, 2021 findings demonstrated that Dose Level 0 was not tolerable, but Dose Level -1 was tolerable. Therefore, patients enrolling to the randomized two arm portion of the trial will receive:**

**Arm 1 LY3214996 200 mg QD and 600 mg HCQ BID and  
Arm 2 LY3214996 400 mg QD**

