#### 5.1.4 Treatment Cross-Over

Participants who are enrolled to **Arm 2** who experience radiologic disease progression on monotherapy will have the option to cross-over to receive treatment with the combination. Cross-over will occur at the treating investigator's discretion following consultation and approval from the overall principal investigator. Participants who cross-over must meet all of the following criteria:

1. The participant does not meet any other investigational product discontinuation criteria (see **Section 5.5**).
2. ECOG performance status is  $\leq 1$ .
3. Absence of rapid disease progression or threat to vital organs/critical anatomical sites (e.g. spinal cord compression) requiring urgent alternative medical intervention.
4. The participant must have a tumor imaging assessment and EKG prior to initiating cross-over treatment (within 28 days of the start of combination dosing). All subsequent assessments will continue with the same frequency defined in the **Study Calendar** and **Section 11**.

5. Participants must re-consent prior to treatment cross-over.

The treating investigator should ensure that patients do not have any significant, unacceptable, or irreversible toxicities indicating that continuing treatment will not benefit the patient.

Participants should be made aware of the potential risks of initiating combination therapy by the treating investigator and must provide re-consent prior to the beginning of cross-over therapy.

Participants who cross-over will receive LY3214996 and HCQ at the dose being administered to **Arm 1** participants. Under no circumstances may a participant crossing-over receive treatment with HCQ at a dose level higher than what is being evaluated on **Arm 1**. Participants enrolled to **Arm 2** who cross-over will not be considered one of the six required participants for the safety analysis of **Arm 1** (see **Section 5.1.3.1**). In the event combination dosing was not found tolerable during the safety lead-in, no treatment with HCQ will be permitted.

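### Cross-over to HCQ 600 mg BID is not held until the Arm 1 safety review of that dose is complete

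*Combined protocol and SAP*

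**What the plan says.** **Lead-in doses.** Dose Level 0 was LY3214996 400 mg QD with HCQ 400 mg BID. The footnote to Table 2 (Section 5.1.1) fixes the fallback level: "The principal investigator determined dose level -1 to be LY3214996 200 mg PO QD and HCQ 400 mg PO BID". Section 5.1.3.1 records that Dose Level 0 was not tolerable and Dose Level -1 was.

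**Arm 1 dose and pause.** Arm 1 therefore opens at LY3214996 200 mg QD with HCQ 600 mg BID. After six evaluable participants, Arm 1 enrollment "will be paused for an assessment of safety of the increased dose of HCQ". The check takes place once all six have completed at least one cycle, and Section 5.1 states: "A treatment cycle will be defined as 28 consecutive days". On the decision, Section 5.1.3.1 says: "The overall principal investigator will review applicable adverse event data and determine if enrollment should continue with HCQ at the 600 mg dose level". Any reduction is at that investigator's discretion and applies to participants still to be accrued to the arm.

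**Cross-over.** Section 5.1.4 says: "Participants who cross-over will receive LY3214996 and HCQ at the dose being administered to" Arm 1. Its cap reads: "Under no circumstances may a participant crossing-over receive treatment with HCQ at a dose level higher than what is being evaluated on" Arm 1. Cross-over is at the treating investigator's "discretion following consultation and approval from the overall principal investigator". The listed conditions cover discontinuation criteria, ECOG status, absence of rapid progression, imaging and EKG, and re-consent. None refers to the Arm 1 review. Cross-over participants do not count toward the six.

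**The concern.** The plan treats the step from HCQ 400 mg to 600 mg BID alongside LY3214996 as one to check before more people are enrolled to it. It sets a number (six), a minimum observation time (one cycle) and a pause. The pause stops only new enrollment to Arm 1, and cross-over from Arm 2 is a second route to the same doses. The cap in 5.1.4 does not close that route, because it is set at the dose under evaluation rather than at a dose already cleared. Until the review is done, the dose under evaluation is 600 mg BID.

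At stake is exposure. Participants beyond the planned six could start a pairing that was not given in the lead-in, before or during the interval the plan sets aside to look at it.

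**Working it through.** **1. The plan's own toxicity figure.** Table 15 gives the chance that the lead-in rule (fewer than 2 DLTs among 6) is passed. With X ~ Bin(6, p), P(X ≤ 1) = (1 − p)^6 + 6p(1 − p)^5.

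| True DLT rate p | P(X ≤ 1) | Table 15 | P(X ≥ 2) |
|---|---|---|---|
| 0.05 | 0.967 | 0.97 | 0.03 |
| 0.1 | 0.886 | 0.89 | 0.11 |
| 0.2 | 0.655 | 0.66 | 0.34 |
| 0.4 | 0.233 | 0.23 | 0.77 |

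At p = 0.01 the result is 0.9985, against >0.99 in the table. Table 15 reproduces. It describes the lead-in at HCQ 400 mg BID. The Arm 1 review has no stated count, so no such table can be computed for it.

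**2. Doses side by side.**

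| Stage | LY3214996 QD | HCQ BID | Status |
|---|---|---|---|
| Dose Level 0 | 400 mg | 400 mg | Not tolerable |
| Dose Level -1 | 200 mg | 400 mg | Tolerable |
| Arm 1 | 200 mg | 600 mg | Reviewed after six evaluable participants |
| Cross-over | as Arm 1 | as Arm 1 | Not linked to that review |

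The last two rows carry an HCQ dose 50% above the cleared level (600/400 = 1.5).

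**3. Can cross-over come before the review?** Let s be the start day of the sixth evaluable Arm 1 participant and a the start day of an Arm 2 participant.

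- Earliest review: s + 28 (one 28-day cycle; Sections 5.1 and 5.1.3.1).
- First scheduled Arm 2 scan: 8 weeks ± 7 days (Table 12 and Section 11.1). Earliest a + 56 − 7 = a + 49; nominal a + 56; latest a + 63.
- The scan precedes the earliest review when a + 49 < s + 28, that is, when s − a > 49 − 28 = 21 days. At the nominal scan date the gap is 56 − 28 = 28 days; at the latest it is 63 − 28 = 35 days.

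These gaps mark when a scan could fall, not when HCQ would start. Progression, approval, the EKG and re-consent must follow, so in practice a somewhat larger gap is needed. A review held later than day 28 works the other way.

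**4. Is a gap above 21 days unusual?** Section 13.2 expects up to 52 participants in 24 months, or 52/24 ≈ 2.2 a month. On the assumption of even accrual with 1:1 allocation, six in Arm 1 means about 12 randomized, which takes 12/(52/24) ≈ 5.5 months. A 21-day gap would then be ordinary. This shows only that the timing condition can be met. The documents give no rate for progression, eligibility or uptake of cross-over, so no number of early cross-overs can be derived.

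**5. Effect of a hold on the primary endpoint.** Section 13.3.2 leaves cross-over participants out of the primary analysis of the combination. Their HCQ starting dose therefore cannot change the 3-of-20 decision in Arm 1.

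**The case against.** The strongest reply is that this is a disclosed choice with safeguards. Section 5.1.4 foresees cross-over while the Arm 1 dose is still under review: it caps HCQ and keeps cross-over participants out of the six. The overall principal investigator runs the Arm 1 review, approves every cross-over and receives adverse event reports (Section 7.4.2), so that person can defer a case. Cross-over participants follow Table 11, with visits and EKGs on days 8, 15 and 22 of cycle 1, and the Section 6 dose rules apply. Their assigned LY3214996 dose falls from 400 to 200 mg. Section 2.3 reports similar tolerability of HCQ 400 and 600 mg BID as monotherapy, and use of 600 mg BID with gemcitabine-based chemotherapy.

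All of this stands and narrows the point. It does not close it: deferral is possible but not required, and none of the cited HCQ experience is with LY3214996.

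A reader might infer more than the documents support:

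- *That sections contradict each other, or that cross-over toxicity is hidden from the review.* No sections conflict, and Section 7.4.2 brings those events to the overall principal investigator.
- *That the Arm 1 decision cannot be checked afterwards because no DLT count is stated.* The DLT list is confined to the lead-in ("Dose-Limiting Toxicities (Applicable for Safety Lead-in Cohort Only"), so a preset threshold is indeed missing. However, all adverse events go on case report forms (Section 7.7) and the DSMC monitors toxicity (Section 12.2), so the data for an audit exist.
- *That a binding 2-of-6 rule with DSMC agreement is needed.* It is a debatable trade against disclosed discretion. It would cut the dose with probability 0.34 at an assumed true DLT rate of 0.2. Section 12.2 gives the DSMC no approval step and foresees reviews up to four times a year, so waiting for agreement could lengthen the pause.
- *That 400 mg is as effective as 600 mg.* The monotherapy study behind that comparison showed negligible activity (Section 2.1), so it says little about the combination.

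**Conclusion.** The gap is real and small. Participants can cross over to LY3214996 200 mg QD with HCQ 600 mg BID before and during the pause meant for checking that pairing, and only case-by-case judgment stands in the way. The timing result rests on the plan's scan schedule and cycle length: an Arm 2 start more than 21 days before the sixth evaluable Arm 1 start is enough for a first scheduled scan to precede the earliest review. It assumes scans on schedule and a review as early as allowed. The number affected is unknown and may be few. No stated figure is wrong, and the efficacy decision is not touched. This is an optional, low-cost improvement.

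**What to change.** In Section 5.1.4, state three things:

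1. Until the Arm 1 review is complete, cross-over participants start HCQ at no more than 400 mg BID, the level cleared with LY3214996 200 mg QD.
2. After the review, cross-over uses the dose then open for Arm 1 enrollment. This also settles a reading problem: a reduction applies only to later Arm 1 accruals, so earlier participants could still be on 600 mg and Arm 1 could have two doses in use.
3. Whether participants who crossed over at 400 mg BID may move to 600 mg BID once it is cleared. Section 6.2 provides for re-escalation only after a reduction, so it does not answer this.

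The cost is a few sentences, with no added participants or visits. The downside is a lower starting HCQ dose for a few early cross-over participants; the primary analysis does not change.

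Optionally, and separate from this fix, the overall principal investigator could use the Section 5.1.2 DLT list as a guide in the Arm 1 review and record the basis for the decision.

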#### 5.1.3.2 Arm 2 Treatment: LY3214996

Participants enrolled to **Arm 2** will receive treatment with LY3214996 at the recommended phase II dose of 400 mg PO once daily.

#### 5.1.4 Treatment Cross-Over

Participants who are enrolled to **Arm 2** who experience radiologic disease progression on monotherapy will have the option to cross-over to receive treatment with the combination. Cross-over will occur at the treating investigator's discretion following consultation and approval from the overall principal investigator. Participants who cross-over must meet all of the following criteria:

1. The participant does not meet any other investigational product discontinuation criteria (see **Section 5.5**).
2. ECOG performance status is  $\leq 1$ .
3. Absence of rapid disease progression or threat to vital organs/critical anatomical sites (e.g. spinal cord compression) requiring urgent alternative medical intervention.
4. The participant must have a tumor imaging assessment and EKG prior to initiating cross-over treatment (within 28 days of the start of combination dosing). All subsequent assessments will continue with the same frequency defined in the **Study Calendar** and **Section 11**.

5. Participants must re-consent prior to treatment cross-over.

The treating investigator should ensure that patients do not have any significant, unacceptable, or irreversible toxicities indicating that continuing treatment will not benefit the patient.

Participants should be made aware of the potential risks of initiating combination therapy by the treating investigator and must provide re-consent prior to the beginning of cross-over therapy.

Participants who cross-over will receive LY3214996 and HCQ at the dose being administered to **Arm 1** participants. Under no circumstances may a participant crossing-over receive treatment with HCQ at a dose level higher than what is being evaluated on **Arm 1**. Participants enrolled to **Arm 2** who cross-over will not be considered one of the six required participants for the safety analysis of **Arm 1** (see **Section 5.1.3.1**). In the event combination dosing was not found tolerable during the safety lead-in, no treatment with HCQ will be permitted.

